
Specific Aim 2. Evaluate the effectiveness of KanSurvive-ECHO for enhancing evidence-based survivorship care for rural breast, colorectal, lung, and prostate cancer survivors. Hypothesis: Compared to delayed intervention control, rural primary care practices randomized to KanSurvive-ECHO will demonstrate greater concordance with evidence-based survivorship care guidelines as measured by a composition score determined by change in EHR documentation consistent with guideline concordant care.

Specific Aim 3: Utilizing the Integrated Promoting Action on Research Implementation in Health Services (i-PARIHS) framework (6) describe key facilitators and barriers to implementation of KanSurvive-ECHO including innovation, recipients, context, and facilitation. This novel project will provide a model for development of a community of practice using practice facilitation and Project ECHO to improve the management and follow-up of cancer survivors in the acute and extended phases of cancer survivorship.

B. Background and Significance

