
Approach: Research Design will include observational research plus pilot testing of the KanSurvive-ECHO intervention

Conceptual Framework: Informed by the Integrated Promoting Action on Research Implementation in Health Services (i-PARIHS) implementation framework, the KanSurvive intervention will target EBP improvement in rural primary care. Our recent pilot work using an updated 4-session case-based curriculum relied on utilization of practice facilitators providing on-site training to rural primary care teams. This project will expand to move beyond traditional training models, to a hands-on practice re-organization. Additional formative data collection with site visits and practice observation will inform final refinement of the KanSurvive ECHO Intervention. The delayed intervention control and KanSurvive-ECHO practices will be compared on outcomes specified by the RE-AIM evaluation framework (e.g., Reach, Effectiveness, Adoption, Implementation fidelity and acceptability, and Maintenance after 6 months).

Study Design: Using a Hybrid Type II study design, (51) the proposed study includes a three-aim plan for further assessing the rural practice environment and refining the KanSurvive-ECHO intervention (Aim 1), testing the effectiveness of KanSurvive-ECHO (Aim 2), and describing key facilitators and barriers to adoption of KanSurvive-ECHO intervention components in rural primary care (Aim 3). We will recruit 20 rural (defined using RUCA-UR codes) primary care practices from the KPEPPER network for a delayed intervention control trial.

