Rural Primary Care Clinics: We have experience recruiting rural primary care clinics across all of rural Kansas. The Kansas Patients and Providers Engaged in Prevention Research (KPPEPR) network is a practice-based research network that has served as host to four previous NIH R01-funded trials. The Board of the network has unanimously agreed to support this project, (see letter of support). They have advised us that they believe we will have no difficulty recruiting the twenty practices needed for this study. We will identify clinics that care for an average of 200 patients that are survivors of breast, colon, lung or prostate cancer. This volume will allow participating practices to observe meaningful changes in patient survivorship care implementation and outcomes. From our pilot work, primary care providers described sending almost all (~95%) of their newly diagnosed cancer patients to the same, local oncology providers/practices. Currently, no EHR-based mechanisms are in place in any of the pilot practices we have worked with to systematically identify cancer survivors or to guide survivorship care through best practice alerts, orders sets, health maintenance modules or other tools. However, an improved understanding of the capacity of the participating primary care clinics will be informed by a recently awarded rural supplement to the KUCC cancer center P30 ([name] & [name], co-leads). Data from all participating clinics will be extracted from EHRs by an "honest broker" who will utilize a consistent algorithm across all EMR systems to record evidence of guideline concordant survivorship care. We anticipate receiving a HIPAA waiver to allow such data abstraction without consenting individual patients.

Planning and engagement

Phase 1 In order to address the cross-cutting implementation barriers in caring for cancer survivors identified in the pilot, (55) we propose to formally describe care gaps, infrastructure needs and processes of care for acute and chronic cancer survivorship in rural primary care focusing on breast, colorectal, lung, and prostate cancer survivors and utilize this formative information to further refine the KanSurvive intervention, including the practice facilitation and Project ECHO approaches.

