2. *Effectiveness* will be measured as % change in electronic health record evidence of guideline concordant care from pre- to 6-months post- KansSurvive-ECHO in intervention versus delayed intervention control practices. Using baseline EHR assessments in charts of cancer survivors identified from hospital registries we will compare the pre- and post- percentages of these survivors with best practice alerts, orders sets, health maintenance modules or other tools that note specific survivorship care services that they should be receiving to meet guidelines (Table 3) (67-74)

3. *Adoption* will be measured by calculating the representativeness of the participating rural primary care practices. Specifically, participating rural primary care practices will be measured on their size and their patient panels and will be compared as a group to the overall data that is available for all rural primary care practices in the state of Kansas on these key variables to assess for the representativeness of participating practices.

4. *Implementation Consistency: In addition to project feasibility and acceptability, we will assess facilitators and barriers to KansSurvive adoption using the i-PARIHS framework (Aim 3). Fidelity:* We will refine KansSurvive fidelity assessment consistent with Schoenwald et al.(55): (1) identifying relevant components for monitoring across practice facilitation and ECHO components (e.g., specificity, necessity, degree of precision), (2) determining who would provide the ratings, (3) obtaining the ratings, and (4) creating a summary score for the ratings. We will monitor fidelity to the KansSurvive components, with checklists associated with practice facilitation from multiple perspectives (e.g., participating practice teams, facilitators, ECHO subject matter experts). *Attendance and Participation.* Percent attendance will be

calculated for each rural primary care practice as the percent of practice facilitation and ECHO sessions attended divided by the total number of sessions offered. For both groups' participation the amount of between session work completed (as a percent).

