5. **Maintenance:** Our experienced team will conduct structured interviews with participating rural primary care practices to assess their ability to sustain key components of the KanSurvive ECHO program over time and maintain effects at 6-months, including policies and procedures to support the cancer survivorship guidelines. Identification of cancer survivors with breast, lung, colon and prostate cancer. In order to identify survivors under the care of a particular PCP, we will engage the local/affiliated hospital's tumor registry. A list of all primary care providers participating in the intervention will be compiled using several key fields: "following doctor" (primary care provider) and the type of cancer (breast, colon, lung, and prostate cancer). This PCP list will be given to local hospitals, which will run a report to identify all cancer survivors with breast, lung, colon and prostate cancer affiliated with the "following doctor". Additional variables from the tumor registry will include demographics, stage, treatment, treating oncologist. Each primary care provider participating in the intervention will receive their list of affiliated patients. (75)

Data extraction will be completed by an "honest broker" who will utilize a consistent algorithm across all EMR systems to record evidence of guideline concordant survivorship care through a HIPAA waiver to allow such data abstraction without consenting individual patients. Medical record extraction is considered the "gold standard" and will be the primary objective data source for this trial. Practice-level data gathered from participating practices will be recorded directly into a secure KUMC REDCap database which requires username and password verification. Only designated research staff will have access to research information. The data collection survey tool built in REDCap will be pilot tested internally and modified as needed to ensure clarity for the data collector.

Table 3: Measure change in EHR documentation Concordant with Evidence-based Cancer Screening by Diagnosis

Cancer Diagnosis	Breast	Lung	Colon	Prostate	EHR Documentation Baseline (Yes/No)	EHR Documentation Post (Yes/No)
Recommended screening based on diagnosis*	Mammogram (annual)	CT (annual)	Colonoscopy (frequency specified by risk)	PSA (annual or more frequent based on risk and time since diagnosis)		
Distress/Depression Screen (PHQ9) (annual)	X	X	X	X		
Lifestyle Recommendations	X	X	X	X		

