76. Centers for Disease Control. Cancer Registry Research Approval Process: Classification of States by Level of Approval Required2018.

ANALYSES

Quantitative Data:

- Differences in cancer survivorship performance indicators before and after intervention were assessed using Chi-square or Fisher Exact tests.
- Clinical characteristics are summarized with frequencies and percentages.
- Demographic and patient characteristics are summarized descriptively with respect to frequencies and percentages for categorical variables, and mean, standard deviation, median, minimum and maximum for continuous variables.
- Differences in surveillance rates by tumor types before and after intervention were assessed using Fisher Exact tests.
- Statistical tests were considered significant if $p < 0.05$.

Qualitative Data:

- Interview notes, transcripts of practice facilitation meetings, and field records were compiled and analyzed using the i-PARIHS framework to evaluate barriers and facilitators to implementation.
- A thematic network analysis was employed by first noting initial impressions.
- Transcripts were independently reviewed line-by-line and preliminary codes were applied to relevant passages.
- A coding framework was developed with clear code descriptions, organizing data into themes and sub-themes.
- This framework was systematically applied to all transcripts using Dedoose software to ensure consistent and meaningful codes across the dataset.

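### Surveillance change is tested separately in each cancer, with no test between cancers and no tumour-specific confidence intervals, so mixed verdicts would not show that the effect differs

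*Combined protocol and SAP*

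**What the plan says.** The quantitative part of the ANALYSES section has one line on surveillance by cancer: "Differences in surveillance rates by tumor types before and after intervention were assessed using Fisher Exact tests". A further bullet sets the significance threshold at p < 0.05 for all tests. Another bullet covers the survivorship performance indicators overall, before versus after, by Chi-square or Fisher test.

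The section lists no test comparing the change between tumour types, no surveillance estimate pooled over types, no confidence intervals, and no rule for reading results that differ by cancer.

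The aim behind this analysis is not tumour-specific. Specific Aim 2 concerns "enhancing evidence-based survivorship care for rural breast, colorectal, lung, and prostate cancer survivors", and its hypothesis rests on one "composition score determined by change in EHR documentation consistent with guideline concordant care". The Effectiveness item under RE-AIM compares change "in intervention versus delayed intervention control practices". In Table 3 the row "Recommended screening based on diagnosis" assigns a different procedure to each cancer: mammogram, CT, colonoscopy or PSA.

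On size, the Study Design paragraph says "We will recruit 20 rural (defined using RUCA-UR codes) primary care practices", and the Rural Primary Care Clinics paragraph says "We will identify clinics that care for an average of 200 patients that are survivors of breast, colon, lung or prostate cancer". The number of charts to be abstracted and the split by cancer are not given.

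**The concern.** Four separate tests give four verdicts. If breast is significant and lung is not, it is natural to conclude that the intervention worked for one and not the other. That does not follow: one p-value below 0.05 and another above it can come from the same true change. Evidence of a difference needs a direct comparison of the changes, and the plan has none. Without confidence intervals, a reader also cannot see how far the four estimates overlap.

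What is at stake is the interpretation of the tumour-type results. Because each cancer has its own surveillance test, readers are likely to compare the verdicts.

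**Working it through.** The plan states no power or sample size by tumour type, so there is no figure to reproduce. The question is how often four tests of the same true change disagree.

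**Inputs from the documents.** Four cancers; p < 0.05 per test (two-sided assumed); 20 practices; an average of 200 survivors per practice. 20 × 200 = 4,000 is a panel-size ceiling, not a stated chart count.

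**Assumptions.** Baseline 60% in every cancer (section A1 gives almost 60%, for mammography only). The same gain in every cancer. Tumour shares either 40/30/20/10% or equal. Before and after treated as independent samples, as the Fisher test does. Four independent tests.

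**Step 1: when mixed verdicts are likely.** With power π in each cancer, P(mixed) = 1 − π⁴ − (1 − π)⁴. This peaks at π = 0.5: 1 − 0.0625 − 0.0625 = 87.5%. It exceeds 50% only for π between 15.9% and 84.1%. At π = 10% or 90% it is 34%, and at 99% it is 4%.

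**Step 2: power per cancer.** Normal approximation: power = Φ[(d − 1.96·s0)/s1], with s0 = √(2p̄(1 − p̄)/n) and s1 = √([p0(1 − p0) + p1(1 − p1)]/n). For the smallest group at 4,000 charts (n = 400, 60% to 65%), s0 = 0.0342 and s1 = 0.0342, so power = Φ(−0.50) = 31%. The groups of 1,600, 1,200 and 800 give 83%, 72% and 54%.

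**Step 3: disagreement at +5 points, 4,000 charts.**
- Split 40/30/20/10: all significant 0.832 × 0.716 × 0.542 × 0.309 = 0.100; none 0.168 × 0.284 × 0.458 × 0.691 = 0.015; mixed 1 − 0.115 = 0.885.
- Equal groups of 1,000 (power 0.637): 1 − 0.637⁴ − 0.363⁴ = 1 − 0.165 − 0.017 = 0.82.

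Equal groups give nearly the same answer, so most of the discordance is chance at moderate power. Unequal size adds a little.

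**Step 4: range.** P(mixed):

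| Charts per reading | Gain | Split, normal | Equal, normal | Split, exact Fisher | Equal, exact Fisher |
|---|---|---|---|---|---|
| 4,000 | +2 | 48% | 48% | not run | not run |
| 4,000 | +5 | 88–89% | 82% | 90% | 83% |
| 4,000 | +8 | 41% | 14% | not run | not run |
| 4,000 | +10 | 17% | 1% | 19% | 1.4% |
| 1,000 | +10 | 88% | 81% | 90% | not run |
| 400 | +10 | 78% | 77% | 72% | 70% |
| 400 | +5 | 38% | 38% | 31% | 30% |

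**Step 5: shared practices.** The four tests use the same practices, so they are positively correlated. I simulated +5 points and 4,000 charts, with practice-level variation in the change common to all four cancers. With assumed SDs of 5, 10 and 15 points, P(mixed) falls to about 82%, 66% and 57% (split) and about 73%, 56% and 45% (equal groups).

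**The case against.** The strongest objection is that mixed verdicts need not be the usual result. They are common only in a window of moderate power, and the documents do not say whether the trial falls there. With all 4,000 charts and +10 points they are uncommon; with few charts and a small gain, most often nothing is significant. The practice-facilitation results cited in the protocol are large (a 100% against a 33% increase in foot examinations; guideline adoption 2.76 times as likely), so +5 points is not an obvious default. This stands, and the claim is limited accordingly.

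A reader might infer that discordance would be mainly an artefact of group size. The equal-group figures do not support that. A reader might also infer that clustering simply lowers power in every group. That would apply to a test that accounts for clustering; an unadjusted Fisher test ignores it, and the effect on disagreement comes through correlated tests.

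A reader might further infer that tumour-specific verdicts will steer dissemination. No section says so: the Innovation section links wider dissemination to key elements of practice change, and the dissemination section refers to i-PARIHS and RE-AIM.

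Separate reporting by cancer also has a reason, since procedures and intervals differ and a common gain is itself an assumption. That supports showing four estimates, but not inferring a difference from four p-values. Finally, the bullet is short, and a comparison across types cannot be wholly excluded, although its before/after wording points to tests within type.

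**Conclusion.** The concern holds in a limited form. As most naturally read, the plan yields four separate verdicts on surveillance and nothing to compare them with. A uniform effect can give discordant verdicts and, at about 16% to 84% power per cancer, usually will. Discordance would therefore not be evidence that the effect differs, and it could not be told apart from chance. This gap depends on no assumed figure.

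How often it would matter does depend on assumptions. The illustrations run from about 1% to about 90% across plausible chart counts and gains, before allowing for shared practices. The documents do not support saying that mixed verdicts are the expected outcome of this trial, or that a tumour-specific finding would more likely be false than true. Because the Aim 2 hypothesis is a single composite across cancers, this affects a secondary analysis. It should be corrected but does not undermine the main aim.

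**What to change.** Replace the separate tests with one model for receipt of the recommended surveillance test. Include tumour type and its interaction with the intervention term; if the randomised comparison is used, that term is period by arm. Allow for clustering by practice and for repeated readings of the same charts, neither of which the Chi-square and Fisher tests handle. With only 20 practices, name a small-sample method. State the effect scale in advance, because whether an effect is uniform depends on it when baseline rates differ between cancers.

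Report the pooled effect and all four tumour-specific differences with 95% CIs. Claim a difference between cancers only from the 3-df interaction test.

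Cost: no new data, but more than one extra term, because the SAP currently contains no model and a clustered one must be specified. The interaction test will have low power, so the conclusion will often be that there is no evidence of a difference by tumour type, with wide intervals. The section is written in the past tense; if the tests have already been run, the model can still be fitted and the estimates reported, labelled as added afterwards.

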Diet/exercise/smoking cessation (annual)						
Review of Family History of Cancer (one time)	X	X	X	X		
Evidence of Changes to "Problem List" (one time, cancer diagnosis or history of)	X	X	X	X		
Evidence of Changes to "Health Maintenance/Preventive Services" or "Order/Smart set" or "Smart Phrases" or "Annual Wellness Visits" Since Cancer Diagnosis (one time)	X	X	X	X		
Treated with Anthracycline Y or N**						
ECHO Cardiogram (frequency specified by risk) **						
Bone Mineral Density (treated with anti-hormone or androgen deprivation therapy) (frequency specified by risk) **						

*if not deemed medically necessary, is their clarification in EHR (e.g., due to type of cancer surgery - total colectomy or bilateral mastectomy)

** exploratory variables: applicable to subset of patients based on treatment exposure

Limitations and strengths to EHR data are inherent to this type of project. There will be cancer survivors missed by the method of using local hospital registries, however, >95% of referrals from our focus group primary care providers are to the same oncologist/practices (49), thus keeping missing cancer survivors to a minimum. Use of a trained honest broker for data extraction will reduce the confounder of a lack of familiarity with EHR and where to find documentation within the EHR also will eliminate potential bias within the practice and patient population.

Study Timeline

Phase/Activity	Year 1	Year 2	Year 3	Year 4	Year 5
----------------	--------	--------	--------	--------	--------

4.9 Dissemination and Future Plans:

Using the i-PARIHS and RE-AIM frameworks for evaluation, relevant findings will be submitted for abstract (poster or presentation) at regional and national meetings and to peer-reviewed

Patient & advisory board engagement	x	x	x	x	x	x	x	x	x	x
Phase 1	x	x	x							
Site recruitment	x	x								
Workflow analysis		x	x							
Assess practice & EHR capabilities + P30 rural supp		x	x							
Explore facilitators & barriers of successful process		x	x					x	x	
Finalize intervention & assessment tools			x	x						
Phase 2				x	x	x	x	x	x	x
Intervention				x	x	x	x			
Wave 1				x	x	x				
Wave 2						x	x	x		
Data extraction							x	x		
Evaluation							x	x		
Data analysis, Dissemination								x	x	
Identify opportunities-sustain community of practice								x	x	

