Location where study will be performed: The study will be performed at KUMC sites. Research staff are located in [name]. Additionally, the rest of the research staff is being supported by the Masonic Cancer Alliance (MCA) located in [name]. Other study activities will be completed online through Project ECHO.

Collaboration (with another institution, if applicable): The MCA will provide research support to complete various phases of the protocol.

Personnel who will conduct the study, including: The sponsor and principal investigators for the study are [name], MPH and [name], MPH.

Assessment of Subject Safety and Development of a Data and Safety Monitoring Plan:

Since this study does not involve any therapeutic intervention we do not anticipate the need for any safety monitoring.

Informed consent process and timing of obtaining of consent: Participating clinics will provide verbal consent to confirm they will participate in the project.

Alternatives to Participation: any of the recruited clinics will have the option to participate or not as the study is completely voluntary.

Costs to Subjects: Participating clinics will not incur any cost while in the project. Participating clinics will get a total of \$1,500 as compensation for their time and participation.

Publication Plan: Results will be published as deemed appropriate by the investigators Drs. [name] and [name].

Bibliography / References / Literature Citation

1. US Census Bureau. Quick Facts: Kansas 2018 [cited 2018]. Available from: <https://www.census.gov/quickfacts/fact/table/ks/PST045217>

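### About 9 to 12 item-level tests are each judged at an unadjusted p<0.05, while the single composite against delayed control that Aim 2 states as its hypothesis is not analysed

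*Combined protocol and SAP*

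**What the plan says.** The Quantitative Data list under ANALYSES is the whole quantitative analysis plan in the document. It has two testing statements and one significance rule:

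- The first testing statement covers the indicators: "Differences in cancer survivorship performance indicators before and after intervention were assessed using Chi-square or Fisher Exact tests"
- The second covers each cancer separately: "Differences in surveillance rates by tumor types before and after intervention were assessed using Fisher Exact tests"
- The significance rule, which applies to both, reads: "Statistical tests were considered significant if $p < 0.05"

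It gives no number of tests, no primary test, no testing order, no sidedness and no multiplicity rule.

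Specific Aim 2 is framed differently. It states one hypothesis, that practices randomised to KanSurvive-ECHO will show greater guideline concordance than delayed-control practices, "as measured by a composition score determined by change in EHR documentation". The Effectiveness entry under Evaluation: RE-AIM also gives one measure, compared between the two arms. Neither measure is labelled primary, the composite has no scoring rule, and neither appears under ANALYSES.

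Table 3 lists the documentation items. One row, "Recommended screening based on diagnosis", takes a different form in each of four cancers, and five further items apply to all four. Two outcome rows, echocardiogram and bone mineral density, carry a double asterisk explained as "exploratory variables: applicable to subset of patients based on treatment exposure". ANALYSES does not mention that distinction.

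**The concern.** The hypothesis and the analysis do not meet. Aim 2 asks one question, about one score, between arms. ANALYSES answers a series of separate before-after questions about items and tumour types. Followed as written, the plan produces a set of p-values and leaves the stated hypothesis untested.

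Multiplicity follows from that omission. A 5% level governs one test; it does not govern a broad conclusion that survivorship care improved when that conclusion may draw on any of several tests. With no confirmatory test named, the plan gives a reader no way to separate a planned finding from the most favourable item in a list. The Publication Plan adds no safeguard, since it does not commit to reporting every item.

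**Working it through.** The document states no power, number of tests or family-wise error rate, so there is no figure of its own to reproduce.

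**Step 1: count the tests (inferred from Table 3).**

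- Items common to all four cancers: distress or depression screen, lifestyle recommendations, family history review, problem-list change, health-maintenance or order-set change = 5.
- Surveillance by tumour type, one test each for breast, lung, colon and prostate = 4. Running total: 5 + 4 = 9.
- If diagnosis-specific screening is also tested pooled over cancers: 9 + 1 = 10.
- If the two exploratory outcome rows are also tested: 10 + 2 = 12. The anthracycline row records an exposure and is not counted.

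**Step 2: independent tests, each at its nominal level.** For k two-sided tests at 0.05:

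- any false-positive difference: 1 − 0.95^k
- a false-positive improvement: 1 − 0.975^k, because half of each 5% lies in the favourable direction

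Two-sided testing is an assumption, since the plan does not state sidedness.

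| Tests (k) | Any difference | Improvement only |
|---|---|---|
| 9 | 1 − 0.95^9 = 37.0% | 1 − 0.975^9 = 20.4% |
| 10 | 1 − 0.95^10 = 40.1% | 1 − 0.975^10 = 22.4% |
| 12 | 1 − 0.95^12 = 46.0% | 1 − 0.975^12 = 26.2% |

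**Step 3: correlated tests.** The items come from the same patients and practices, so positive correlation is plausible. The document gives no value; a range is assumed. Simulation of equicorrelated normal statistics (400,000 draws) gave, for any difference and, in brackets, improvement only:

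| Correlation | 9 tests | 10 tests | 12 tests |
|---|---|---|---|
| 0.3 | 33% (17%) | 35% (18%) | 40% (20%) |
| 0.5 | 27% (13%) | 29% (14%) | 32% (16%) |
| 0.8 | 17% (8%) | 17% (9%) | 19% (9%) |

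**Step 4: bound without assuming independence.** The bound is k × 0.05: 45% for 9 tests, 50% for 10 and 60% for 12. The independence figures are therefore not strict upper limits.

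**Step 5: comparison with one test.** A single two-sided test at 0.05 has a 5% chance of any false difference and a 2.5% chance of a false improvement. Under independence, the improvement figure is about eight times (20.4/2.5) to ten times (26.2/2.5) as large.

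**The case against.** The strongest reply is that the protocol does have a single focus. Aim 2 states one composite and the RE-AIM section one effectiveness measure, so the item tests can be read as supporting description of process indicators in work that the Approach section itself calls pilot testing. The number of tests is not in the document, two of the rows counted towards 12 are already labelled exploratory, and correlation together with the conservatism of Fisher's test pulls the error rates down. Some pages were not in the text available for review, so a primary outcome named there cannot be excluded.

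Most of this stands as a limit on size. It does not remove the defect: the one measure that could carry a confirmatory test is absent from ANALYSES, and the exploratory label in Table 3 is not carried into the 0.05 rule.

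Three stronger readings are tempting and are not supported:

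- **37% to 46% as the chance of a false improvement.** Those figures count differences in either direction. For improvement alone they would need one-sided tests at 0.05, which the document does not state.
- **Any one significant item counts as trial success.** ANALYSES says when a test is called significant; it sets no success criterion.
- **The publication sentence, "Results will be published as deemed appropriate by the investigators", plans selective reporting.** It is a general statement and says nothing about choosing among items.

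**Conclusion.** The point holds. The plan applies an unadjusted 0.05 to each item and tumour-type test, sets no hierarchy, and does not analyse the between-arm composite on which Aim 2 rests. The missing composite is the more serious part, and the multiplicity is its consequence.

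The size, for 9 to 12 tests that are independent and each hold their 5% level, is a 37% to 46% chance of at least one false-positive difference, or about 20% to 26% for a false-positive improvement with two-sided tests. At an assumed correlation of 0.5 the chance of any difference is 27% to 32%.

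These figures rest on a count inferred from Table 3. They are also a generic calculation and should not be read as this trial's actual error rate: the before-after tests are exposed to secular change, clustering by practice and repeated charts, any of which can move the per-test error away from 5%.

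**What to change.** In the ANALYSES section:

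1. Name the Aim 2 composite, compared between intervention and delayed-control practices, as the only confirmatory test, at two-sided 0.05. State how it is scored; one option is the share of applicable non-exploratory Table 3 items documented per survivor.
2. Report the individual items and the four tumour-type rates as secondary estimates with 95% confidence intervals and no confirmatory significance claim. If tests are wanted, use Holm across the family; with 9 tests the first threshold is 0.05/9 = 0.0056.
3. Report the double-asterisk items descriptively.
4. Commit, there and in the Publication Plan, to reporting all Table 3 items in both arms.
5. ANALYSES is written in the past tense. If item-level tests have already been run, label their p-values exploratory; a hierarchy chosen afterwards would not make them confirmatory.

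The change needs no further sites or data items. Its main work is defining the composite score, which takes more thought than the wording changes. The cost is that individual items can no longer be claimed as confirmed effects at p<0.05.
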